8.8 Early Discontinuation of Patients

Patients may discontinue from the study at any time for any reason. Discontinuation is permanent; once a patient is discontinued, he/she shall not be allowed to enroll again.

Patients can be prematurely discontinued from the study for one of the following reasons:

- AE
- Noncompliance with protocol
- Noncompliance with IP dosing regimen
- Withdrawal of consent (a clear reason must be documented when possible)
- Lost to follow-up (every effort must be made to contact the patient; a certified/traceable letter must be sent)
- Study terminated by sponsor
- Site terminated by sponsor
- Pregnancy
- Other reasons

Notification of early patient discontinuation from the study and the reason for discontinuation will be clearly documented on the appropriate eCRF page. Patients who take IP during the study (OL treatment period or the DB treatment period) and who prematurely discontinue from the study, regardless of cause, should be seen for a final assessment. A final assessment will be defined as completion of the evaluations scheduled for Visit 31/ET. If the patient discontinues after IP is taken, the patient is also expected to return for 2 safety follow-up visits, Visit 32 (2 weeks after completion of the ET visit) and Visit 33 (4 weeks after completion of the ET visit).

At a minimum, collect the following information when a patient discontinues:

- 1. The reason the patient discontinued;
- 2. The date of the last dose of test products from the trial;
- 3. The date of the last assessment and/or contact. A follow-up contact (telephone or visit) will be arranged as appropriate;
- 4. (S)AEs;
- 5. Compliance with the test product administration as specified in this protocol;
- 6. Final Assessments: Unless there is withdrawal of consent, every effort should be made to ensure that all procedures and evaluations scheduled for Visit 31/ET and subsequently Visits 32 and 33 (SFU Period) are performed (Table 1, Schedule of Visits and Procedures).
- 7. Retrieve all IP(s) from the patient.

For all patients who discontinue as a result of being lost to follow-up, a determination must be noted in the eCRF as to whether the loss is related to an acute exacerbation of bipolar disorder.

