9.3 Procedures for Reporting a Serious Adverse Event

Any SAE occurring during the study period (beginning with informed consent) and for at least 30 days after the last dose of study drug must be immediately reported but no later than 24 hours after learning of a SAE. SAEs must be reported to AbbVie (or agent of AbbVie eg, Contract Research Organization) as listed on the AbbVie study contacts list and recorded on the SAE/AESI form. All patients with a SAE must be followed up and the outcomes reported. The investigator must supply the sponsor and the IRB/IEC with any additional requested information (eg, autopsy reports and discharge summaries).

In the event of a SAE, the investigator must:

- 1. Notify AbbVie immediately using the SAE/AESI form (contact details can be found on page 1 of the SAE/AESI form); phone numbers and relevant AbbVie personnel contacts are also on the front page of protocol and study contacts list.
- Obtain and maintain in his/her files all pertinent medical records, information, and medical judgments from colleagues who assisted in the treatment and follow-up of the patient.
- 3. Provide AbbVie with a complete, written description of the adverse event(s) on the SAE/AESI form describing the event chronologically, including any treatment given (eg, medications administered, procedures performed) for the adverse event(s). Summarize relevant clinical information about the event: signs, symptoms, diagnosis, clinical course and relevant clinical laboratory tests, etc. Include any additional or

alternative explanation(s) for the causality which includes a statement as to whether the event was or was not related to the use of the investigational drug.

4. Promptly inform the governing IRB/IEC of the SAE as required by the IRB/IEC, local regulations, and the governing health authorities.

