Safety Follow-up (SFU) Period: Patients who complete the study, or who prematurely discontinue from either the OLTP or DBTP, will be followed for 4 more weeks and will have 2 evaluations for safety assessments at Visit 32 (Week 57) and Visit 33 (Week 59) during the SFU period. During the SFU, patients will receive treatment as usual at the discretion of the investigator or designee. Patients will not receive investigational product (IP) during the SFU period.

IP in the form of capsules packaged in blister packs will be provided by the sponsor. No IP will be administered during the screening/washout period or the SFU period. During the OLTP (up to 16 weeks), patients will take 1 capsule daily. All patients will begin with cariprazine 1.5 mg on Day 1. Patients diagnosed with bipolar I disorder, current episode (ie, index episode) manic with or without mixed features, will receive cariprazine 3.0 mg/d on Day 2 and continue on 3.0 mg/d until the end of the OLTP. Patients diagnosed with bipolar I disorder, current episode (ie, index episode) depressive with or without mixed features, will continue to receive cariprazine 1.5 mg/d from Day 2 to 7. On Day 8, the dose for these patients will be increased to 3.0 mg/d and continue until the end of the OLTP. For the 39-week DBTP, patients will be supplied with identically appearing capsules of either cariprazine 3.0 mg, cariprazine 1.5 mg, or placebo. During the DBTP, patients will take 1 capsule daily. The dosing regimen is presented in the [Table 4-1](#).

Table 4-1. Treatment Regimen and Dosing

Drug/Dose	Investigational Product Frequency	Route of Administration
Open-Label Treatment Period (Week 1)		
Index Episode: Manic (with or Without Mixed Features)		
Cariprazine 1.5 mg Day 1 / Cariprazine 3.0 mg Days 2-7	Once daily	Oral (capsule)
Index Episode: Depressive (with or without Mixed Features)		
Cariprazine 1.5 mg Days 1-7	Once daily	Oral (capsule)
Open-Label Treatment Period (Weeks 2 to 16)^a		
Cariprazine 3.0 mg	Once daily	Oral (capsule)
Double-Blind Treatment Period (Weeks 17 to 55)		
Placebo	Once daily	Oral (capsule)
Cariprazine 1.5 mg	Once daily	Oral (capsule)
Cariprazine 3.0 mg	Once daily	Oral (capsule)

All investigational products will be taken orally as a single daily dose at approximately the same time of day (morning or evening). The dosing time can be switched if there are tolerability problems. Any switch must allow at least 24 hours between 2 consecutive doses and must be documented in the eCRF.

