7.0 STUDY PATIENTS

7.1 PATIENT DISPOSITION

The OLTP starts with the first dose of OLTP and ends with one of the following: the last scheduled assessment at Visit 12 (Week 16) or early termination (ET) before Visit 12 for patients who do not enter the DBTP; or 1 day before the date of the first dose of DBTP (or the date of the first dose of the DB IP if the last scheduled assessment date in the OLTP is on the date of the first dose of the DBTP) for patients who enter the DBTP.

The DBTP starts with the first day of randomization and ends with the last scheduled assessment at Visit 31 (Week 55) or ET.

The SFU period starts one day after the end of the previous period and ends with the last available assessment. For patients without Visit 32 (Week 57) or Visit 34 (Week 59) assessment, the SFU period would not be derived.

Screen-failure patients (ie, patients screened but not included in the OL Safety Population) and the associated reasons for failure will be tabulated overall for the Screened Population.

The number and percentage of patients in the Screened, OL Safety and OL ITT Populations will be summarized overall and by study center. The number and percentage of patients in the Randomized, DB Safety, and DB ITT Populations will be summarized overall by treatment group and by treatment group and study center.

The number and percentage of patients in the OL Safety Population, who prematurely discontinued from the OLTP, who completed the OLTP, who entered the DBTP, and who entered the SFU period will be summarized overall and by reasons for premature discontinuation as recorded on the OL disposition page of the electronic case report forms (eCRF).

Similarly, the number and percentage of patients in the DB Safety Population who completed the DBTP, who prematurely discontinued from the DBTP, and who entered the SFU period will be summarized overall, by DBTP treatment group and by reasons for premature discontinuation as recorded on the DB disposition page of the eCRF. Patients who relapse during the DBTP will also be summarized as completing the study.

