11.1 ADVERSE EVENTS

Aes will be coded by system organ class and preferred term using the *Medical Dictionary for Regulatory Activities* (MedDRA), Version 21.0 or newer.

An AE will be considered a treatment-emergent adverse event (TEAE) if the AE began or worsened (increased in severity or became serious) on or after the date of the first dose of OL IP. Per eCRF instructions, a new AE record will be created with a new AE onset date for any AE that worsens. Therefore, TEAEs can simply be identified as those Aes with recorded onset date (and time, if known) on or after the date of the first dose of IP.

The number and percentage of patients reporting TEAEs during the OLTP will be tabulated by system organ class and preferred term; by system organ class, preferred term, and severity; and by system organ class, preferred term, and relationship to IP.

The number and percentage of patients reporting TEAEs during the DBTP will be tabulated for each treatment group by system organ class and preferred term; by system organ class, preferred term, and severity; and by system organ class, preferred term, and relationship to IP. The total number and percentage of TEAEs during the DBTP will also be summarized by severity and relationship to IP for each treatment group.

The number and percentage of patients reporting TEAEs during the OL SFU period will be tabulated by system organ class and preferred term for the OL Safety Population. The number and percentage of patients reporting TEAEs during the DB SFU period will be tabulated by system organ class, preferred term, and DB treatment group for the DB Safety Population.

For OLTP, DBTP, or SFU period, if more than 1 AE was coded to the same preferred term for the same patient, the patient will be counted only once for that preferred term using the most severe and most related occurrence for the summarization by severity and by relationship to IP.

An AE that occurs more than 30 days after the date of the last dose of DB IP or occurs after the last SFU visit (whichever comes last) will not be summarized except for Aes related to reported pregnancies. Aes associated with pregnancies reported in the protocol-required timeframe up to approximately 12 weeks following the last dose of DB IP will be summarized.

The number and percentage of patients with common ($\geq 2\%$ of patients in any treatment group) TEAEs will be summarized by preferred term for OLTP and be summarized by preferred term and treatment group for DBTP.

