
The number and percentage of TEAEs leading to premature discontinuation of IP during the OLTP will be summarized by preferred term. The incidence of Aes leading to premature discontinuation of IP during the DBTP will be summarized by preferred term and treatment group.

An AE will be considered a treatment-emergent serious adverse event (TESAE) if it is a TEAE that additionally meets any serious adverse event (SAE) criterion.

Summary tables will be provided for patients with TESAEs if these occurred in 5 or more patients. The number and percentage of patients with TESAEs will be summarized for OLTP, DBTP, and SFU period.

For the Screened Population, listings will be presented for patients with SAEs, patients with Aes leading to premature discontinuation, and patients who die (if any). All patients with SAEs, including SAEs reported during the screening period and the SFU period, and patients discontinuing because of Aes occurring before the start of OLTP will be included in these listings.

The number and percentage of patients with EPS TEAEs, EPS SAEs, and EPS Aes leading to premature discontinuation of IP will be summarized overall for the OLTP in the OL safety population and by treatment for the DBTP in the DB safety population separately.

The number and percentage of patients reporting TEAEs of ocular events of special interest will be summarized overall for the OLTP in the OL safety population and OL SFU period in the OL SFU population, by treatment for the DBTP and DB SFU in the DB safety population. A listing of all reported ocular events of special interest will be provided.

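### SAP 7.1 derives no safety follow-up period for patients without a follow-up visit, which conflicts with the date-based AE cut-off in SAP 11.1 and can leave late events in no period table

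*SAP*

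**What the plan says.** **Periods.** SAP 7.1 is the only visible place that sets period boundaries. The double-blind period "ends with the last scheduled assessment at Visit 31 (Week 55) or ET", and the open-label period of a patient who is not randomised also closes at the last scheduled or ET assessment. The SFU period begins the next day and closes at the last available assessment. Then comes the exception: "For patients without Visit 32 (Week 57) or Visit 34 (Week 59) assessment, the SFU period would not be derived".

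**Visits.** SAP 4.0 places the "safety assessments at Visit 32 (Week 57) and Visit 33 (Week 59) during the SFU period". Neither schedule contains a Visit 34.

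**Tables.** SAP 11.1 tabulates TEAEs separately for the open-label period, the double-blind period, the open-label SFU and the double-blind SFU. For serious events: "The number and percentage of patients with TESAEs will be summarized for OLTP, DBTP, and SFU period". SAP 11.0 sets the SFU denominators as the whole open-label SFU population or the whole double-blind safety population, with no restriction to patients who have an SFU period.

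**Cut-off.** SAP 11.1 has its own exclusion. It begins "An AE that occurs more than 30 days after the date of the last dose of DB IP", adds events after the last SFU visit, and applies whichever limit comes last. Pregnancy-related AEs are exempt.

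**Collection.** Under protocol 9.3, SAEs arising during the study and "for at least 30 days after the last dose of study drug must be immediately reported". Attendance plays no part.

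**Listings.** SAP 11.1 lists SAEs, AEs leading to discontinuation and deaths for the Screened Population, including SAEs from the SFU period.

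**The concern.** Two sections give different answers to one question: up to when does an event after treatment count? In 7.1 the answer depends on attendance, and in 11.1 on dates. A programmer who builds the period variables from 7.1 gets no SFU window for a patient who had the ET visit and then did not return. A TEAE or treatment-emergent SAE in that patient in the following weeks, including a fatal one, has no period to be counted in. The patient still sits in the denominator, so the SFU incidence is biased downwards.

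Both study objectives include safety, and the four-week follow-up is there to observe patients after drug is stopped. The double-blind SFU table is by arm, so any difference between arms in attendance would carry into it. In addition, SAP 11.1 produces treatment-emergent SAE summary tables only when at least 5 patients are affected, so a few uncounted events could decide whether a table appears. The choice between the two rules should be written down before unblinding.

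**Working it through.** The plan gives no figure on this point to reproduce. The check covers the visit label, the readings of the rule, and the days left unassigned.

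**1. Which visit is Week 59?** Study days are from protocol Table 1 and SAP Table 4-2; week = (day − 1)/7.
- Visit 31: Day 386, 385/7 = 55.
- Visit 32: Day 400, 399/7 = 57, which is 14 days after Visit 31.
- Visit 33: Day 414, 413/7 = 59, which is 28 days after Visit 31.

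Protocol 8.8 also puts Visit 33 four weeks after ET. So Week 59 is Visit 33, and Visit 34 is a label error.

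**2. Who gets an SFU period?** The word joining the two visits can mean that the period is withheld when neither visit took place, or when either is missing.

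| Attended | As printed, neither | As printed, either missing | With Visit 33, neither | With Visit 33, either missing |
|---|---|---|---|---|
| None | no | no | no | no |
| Visit 33 only | no | no | yes | no |
| Visit 32 only | yes | no | yes | no |
| Both | yes | no | yes | yes |

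The sensible reading (neither, with Visit 33) covers 3 of 4 patterns. Correcting the label restores patients seen only at Visit 33. It does nothing for those seen at neither visit.

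**3. Days unassigned under that reading.** Assume that the last dose is on the Visit 31 day (Day 386), visits are on schedule, and the last available assessment is the last attended visit. The 30-day limit in 11.1 is then 386 + 30 = Day 416.
- No follow-up visit: Days 387 to 416, or 30 days.
- Visit 32 only: the SFU ends on Day 400, so Days 401 to 416, or 16 days.
- Both visits: the SFU ends on Day 414, so Days 415 and 416, or 2 days.

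Each day by which the last dose precedes the ET assessment shortens these gaps by one day. Events between last dose and ET are not lost, because the treatment period runs to ET.

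**4. Does another table recover the events?** SAP 11.1 plans no whole-study TEAE or treatment-emergent SAE table, and none for last dose plus 30 days. The listings recover SAEs, deaths and discontinuation AEs as cases, without a rate. Other non-serious TEAEs in the gap are not recovered.

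**5. Two related gaps.** The 11.1 cut-off names only double-blind drug, so it gives no last-dose date for patients who were never randomised. And 7.1 sets no end date for the treatment period of a patient with no Visit 31/ET, so the SFU start is undefined too.

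**6. Size, as illustration only.** The documents give no follow-up attendance rate. Let m be the share attending no follow-up visit, assumed to be 5% to 26%.
- Randomised: 378 × 0.05 = 18.9 and 378 × 0.26 = 98.3, so about 19 to 98 patients.
- Open-label, not randomised: 822 − 378 = 444; 444 × 0.05 = 22.2 and 444 × 0.26 = 115.4, so about 22 to 115. (Protocol 4.1 gives 822. SAP 14.0 prints 882, but its own rates give 1245 × 0.66 = 821.7 and 822 × 0.46 = 378.1.)
- If risk is unrelated to attendance, tabulated incidence = true incidence × (1 − m). For an assumed true 2%, that is 0.02 × 0.95 = 1.9% down to 0.02 × 0.74 = 1.5%.

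These are patients without a period, not lost events. A patient with no event after ET loses nothing from the tables.

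**The case against.** The best defence is that the sentence sits in the disposition section, where patients entering follow-up are counted. Withholding an SFU period from someone never seen in follow-up is reasonable for that count. Nothing says that AEs are assigned by this derivation. The AE section has its own onset-date rules, and the specific rule may govern. The protocol points the same way, since 7.3.4.1 counts SAEs as on-therapy up to 30 days after last dose. SAP 16.2 also places late eye examinations by date. The SFU visit windows (Table 16.1-10) and the table specifications are not visible to us and might settle it. This stands as a limit on certainty: the loss is inferred. It does not remove the conflict, because no other period definition is visible and a programmer must still choose.

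Stronger readings are tempting and do not hold:
- **That deaths drop out of the tables.** No death table by period is planned; deaths are listed for all screened patients. At most, a fatal event is missing from the treatment-emergent SAE count.
- **That all post-treatment events go unreported.** Only those after the ET/Visit 31 assessment are at risk, and the SAEs among them stay in the listings. Potential Hy's Law cases in the double-blind population have their own 30-day window.
- **That every SFU table would be empty.** This needs the either-missing reading together with literal coding of a visit that does not exist. The printed week identifies Visit 33, and a programmer would query it.
- **That the worst outcomes are removed selectively.** A serious event may well prevent attendance, but the documents give no evidence on this, and protocol 9.3 requires every SAE to be followed up.
- **That 7.1 breaches protocol 9.3.** That section governs collection and reporting to the sponsor, not tabulation.

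**Conclusion.** The concern holds as an unreconciled conflict between SAP 7.1 and 11.1, together with a wrong visit number. Read literally, 7.1 leaves up to 30 days per patient in no period for those with an ET/Visit 31 assessment and no follow-up visit. TEAEs and treatment-emergent SAEs starting then are absent from the period tables, while the denominators are unchanged. Shorter gaps arise for patients who attend only one visit. This assumes that the AE tables use the 7.1 periods, which the SAP implies by defining periods nowhere else but does not state.

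The number of patients or events affected cannot be derived from the documents; the ranges above rest on assumed attendance and incidence. Primary efficacy and the safety tables for the treatment periods up to ET are not touched where that visit took place. I would class this as should-fix, before unblinding.

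**What to change.** In SAP 7.1 and 11.1:
1. Change Visit 34 to Visit 33.
2. Assign post-treatment AEs and SAEs by onset date to the open-label SFU (not randomised) or the double-blind SFU (randomised). The window runs from the day after the last treatment period ends to the later of 30 days after the last dose of open-label or double-blind drug and the last SFU visit, regardless of attendance. Extend the 11.1 cut-off to open-label drug in the same words.
3. Where there is no Visit 31/ET, end the treatment period at the later of the last dose and the last assessment.
4. Base the disposition count of patients entering follow-up on actual attendance or the eCRF, so that the date-based window does not make it nearly universal.
5. State where pregnancy-related AEs, which 11.1 follows for about 12 weeks, are shown.

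The cost is a short text change and one derivation step, with no new data. Reported SFU event rates may come out slightly higher.
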